-  CSQ-Overall is to be administered only if patient received treatment to midsection (abdomen and flank) plus at least one additional specific body area. The CSQ-Overall should be completed at visit where at least 12-weeks have passed since the final treatment session for all the treated body areas. For example, if the participant receives only one treatment session for one specific body area but two treatment sessions for another specific body area, the CSQ-Overall should be administered at Visit 9 where all the treated areas will have undergone at least a 12-week post treatment period.
-  The CGPQ should be completed at visit where at least 12-weeks have passed since the final treatment session for all the treated body areas. For example, if the participant receives only one treatment session for one specific body area but two treatment sessions for another specific body area, the CGPQ should be administered at Visit 9 where all the treated areas will have undergone at least a 12-week post treatment period.
-  The 12-week post final treatment CPIQ should be completed at visit where at least 12-weeks have passed since the final treatment session for all the treated body areas. For example, if the participant receives only one treatment session for one specific body area but two treatment sessions for another specific body area, the CPIQ should be administered at Visit 9 where all the treated areas will have undergone at least a 12-week post treatment period.

Should it ever become necessary to remain isolated at home or to shelter-in-place per local, regional, or state orders, study visits may be impacted. This may include changes such as phone or virtual visits, visits at alternative locations, or changes in the visit frequency and timing of study procedures, among others. Additional details are provided throughout Section 8. Every effort should be made to ensure the safety of participants and site staff, while maintaining the integrity of the study. If visits cannot be conducted onsite due to travel restrictions or other pandemic or natural disaster-related reasons, follow the modifications provided throughout Section 8.

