### 7.1. Discontinuation of Study Intervention

During the treatment, study intervention may be discontinued due to significant discomfort, wellness issues, psychological issues, or the participant's refusal to continue the treatment.

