### 9.3. Populations for Analyses

The following populations are defined for statistical analyses:

Population	Description
Enrolled	The enrolled population will consist of all participants who sign the informed consent.
Safety	The safety population will consist of all enrolled participants who receive a cryolipolysis treatment cycle (started or completed).
Evaluable	
 
The evaluable population for the primary endpoint will consist of all treated participants who completed the cryolipolysis treatment plan to the midsection and who completed the CSQ-Midsection Item 1 at 12 weeks after the final treatment measured at Visit 8 (Week 12) for participants who receive 1 treatment session and at Visit 9 (Week 20) for participants who receive 2 treatment sessions.
 
The evaluable population for other effectiveness endpoints will consist of all treated participants who completed the cryolipolysis treatment plan for any other body areas (whether midsection treatment completed or not).
 

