#### 9.4.3. Secondary Effectiveness Endpoints

- The proportion of participants who received treatment to abdomen and flank and one or more additional body areas for treatment with “satisfied” or “very satisfied” on CSQ-Overall Item 1 measured at Week 12 (Visit 8,12-week follow-up for participants who receive only 1 treatment session to all treated body areas) or at Week 20 (Visit 9, 12-week follow-up for participants who receive 2 treatment sessions to any or all treated body areas).
- The proportion of participants with “satisfied” or “very satisfied” on individual treated body area (upper arms, inner thighs, outer thighs, fat under chin) CSQ Item 1 measured at Week 12 (Visit 8, 12-week follow-up for participants who receive only 1 treatment session) or at Week 20 (Visit 9,12-week follow-up for participants who receive 2 treatment sessions) for the respective treated body areas.
- Correct identification of baseline vs 12-week post-final treatment images of the treated body area(s) by at least two out of three blinded, independent reviewers for the following body areas:
  - Midsection
  - Upper arms
  - Inner thighs
  - Outer thighs
  - Submental area

Success will be defined as at least 70% correct identification of the pre-treatment images.

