### 4.0 Analysis Populations

The following population sets will be used for the statistical analyses.

The Enrolled Population will consist of all participants who signed the informed consent.

The Safety Population will consist of all enrolled participants who received at least one cryolipolysis treatment cycle (started or completed).

The Evaluable Population 1 will consist of all participants who completed the cryolipolysis treatment plan to the midsection and completed the CSQ-Midsection Item 1 at 12 weeks after the final treatment measured at Visit 8 (Week 12) for participants who receive 1 treatment session, or at Visit 9 (Week 20) for participants who receive 2 treatment sessions, or at 12 weeks +14 days post treatment session 2 for participants who had their treatment session 2 rescheduled because of the CoolSculpting® Elite treatment hold in the US on / after 24th August 2021, and do not have any significant protocol deviation or violation.

The Evaluable Population 2 will consist of all participants who completed the cryolipolysis treatment plan for any other body areas (Upper Arms, Inner Thighs, Outer

Thighs and Submental Area) whether midsection treatment is completed or not, and do not have any significant protocol deviation or violation .

The Evaluable Population 3 will consist of all participants who completed the cryolipolysis treatment plan for any body areas (Midsection, Upper Arms, Inner Thighs, Outer Thighs and Submental Area) and do not have any significant protocol deviation or violation.

The Evaluable Population 4 will consist of all participants who completed the cryolipolysis treatment plan to the midsection and one or more additional body areas (Upper Arms, Inner Thighs, Outer Thighs and Submental Area) and do not have any significant protocol deviation or violation.

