#### 9.4.2 Main Analyses of Key Secondary Effectiveness Endpoints

The number and percentage of participants with “satisfied” or “very satisfied” on the Item 1 for the CSQ-Overall, CSQ-Upper Arms, CSQ-Inner Thighs, CSQ-Outer Thighs and CSQ-Fat Under Chin, at Week 12 (Visit 8) for participants who receive 1 treatment session, or at Week 20 (Visit 9) for participants who receive 2 treatment sessions, or at 12 weeks +14 days post treatment session 2 for participants who had their treatment session 2 rescheduled because of the CoolSculpting® Elite treatment hold in the US on / after 24th August 2021 will be summarized for the Evaluable Population 4 (overall) and Evaluable

Population 2 (other treated body areas) and the two-sided Fisher's exact 95% CI on the percentage will be provided.

The number and percentage of participants with correct identification of baseline vs 12-week post-final treatment by 2/3 and 3/3 blinded, independent reviewers for the following body areas will be summarized for the Evaluable Population 1 (midsection) and Evaluable Population 2 (other treated body areas) and the two-sided Fisher's exact 95% CI on the percentage will be provided:

- Midsection
- Upper arms
- Inner thighs
- Outer thighs
- Submental area

Listings will be provided for CSQ-Overall, CSQ-Upper Arms, CSQ-Inner Thighs, CSQ-Outer Thighs and CSQ-Fat Under Chin, and correct identification of baseline vs 12-week post-final treatment for the Safety Population.

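### CSQ-Overall is defined and collected for everyone treated on the midsection plus another area, but the SAP reports it only for plan completers without significant deviations

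*SAP*

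**What the plan says.** **Endpoint.** Protocol 9.4.3 defines the first secondary endpoint as "The proportion of participants who received treatment to abdomen and flank and one or more additional body areas for treatment" who answer satisfied or very satisfied on CSQ-Overall Item 1 at the 12-week visit after final treatment. SAP 3.2 and 9.4.1 repeat this denominator.

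**Collection.** Footnote 5 to Protocol Table 1-1, repeated in the SAP schedule, uses the same basis: "CSQ-Overall is to be administered only if patient received treatment to midsection (abdomen and flank) plus at least one additional specific body area".

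**Protocol population.** Protocol 9.3 has one evaluable population for all effectiveness endpoints other than the primary: treated participants who "completed the cryolipolysis treatment plan for any other body areas (whether midsection treatment completed or not").

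**SAP population.** SAP 9.4.2 says that CSQ-Overall "will be summarized for the Evaluable Population 4 (overall) and Evaluable" Population 2 (the individual areas). SAP 4.0 states: "The Evaluable Population 4 will consist of all participants who completed the cryolipolysis treatment plan to the midsection and one or more additional body areas". It adds that members must have no significant deviation or violation. For the individual-area questionnaires, Evaluable Population 2 keeps the protocol's waiver: "whether midsection treatment is completed or not, and do not have any significant protocol deviation or violation".

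**Handling of what is left out.** SAP 9.2 imputes nothing, 8.0 (intercurrent events) and 9.4.3 (sensitivity analyses) are marked not applicable, and 9.4.2 lists CSQ-Overall for the Safety Population.

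**The concern.** CSQ-Overall asks for satisfaction with all treated areas taken together. A participant whose midsection treatment was stopped but who stayed to the final visit is given the form, answers it, and belongs to the endpoint as worded. That answer is then absent from the reported rate.

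The selection acts after treatment has started, and the reasons may be related to the outcome. Protocol 7.1 says that "study intervention may be discontinued due to significant discomfort, wellness issues, psychological issues, or the participant's refusal to continue the treatment". The exclusion for significant deviations is a second restriction that Protocol 9.3 does not contain. SAP 7.5 includes treatment and timeframe deviations among the significant ones.

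At stake is what the published percentage describes: satisfaction among those treated on several areas, or satisfaction among those who finished as planned. No hypothesis is tested, so this is a matter of estimation only.

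**Working it through.** **1. Who counts under each rule.** All participants below received midsection treatment and at least one additional area, and answered the item.

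| Participant | Endpoint text and footnote 5 | Protocol 9.3 | SAP Evaluable Population 4 |
|---|---|---|---|
| Completed midsection and an additional area, no significant deviation | in | in | in |
| Completed an additional area, not the midsection | in | in | out |
| Completed midsection, not the only additional area | in | out | out |
| Completed both, significant deviation | in | in | out |

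Rows 2 and 4 separate the SAP from the protocol. Row 3 is a mismatch inside the protocol itself, between its endpoint and its population. SAP 9.4.1 and 9.4.2 differ on rows 2, 3 and 4.

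Unlike Evaluable Population 1, Evaluable Population 4 does not require an answered item, so the denominator of the percentage is not explicit either.

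**2. The plan's own figure.** Protocol 9.2 and SAP 2.4 give 96 participants for an exact (Clopper-Pearson) 95% CI of width 0.2 at 63.9%. With x = 0.639n, n = 96 gives 0.5346 to 0.7346, width 0.2000, and n = 95 gives 0.2010. With 12% attrition, 96 / 0.88 = 109.1, or about 110. Both figures reproduce. They concern the primary endpoint, and this point does not affect them.

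**3. Possible size.** The documents give neither the number of multi-area participants nor the number excluded. Assumed inputs:
- N = 60 multi-area participants, all answering the item.
- d = 7 excluded by Evaluable Population 4 (12% of 60, rounded). The 12% is borrowed from the attrition allowance and is not a documented non-completion rate.
- Satisfaction among those retained close to the planning rate: 0.639 × 53 = 33.9, taken as 34.

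Rate in Evaluable Population 4: 34/53 = 64.2% (exact 95% CI 49.8 to 76.9).

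Gap between that rate and the rate in all respondents = (d/N) × (rate in retained − rate in excluded):

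| Excluded participants | Rate in all 60 | Gap |
|---|---|---|
| Equally satisfied | 64.2% | 0 |
| Half satisfied | 37.5/60 = 62.5% | 7/60 × (64.15 − 50) = 1.7 points |
| None satisfied | 34/60 = 56.7% (43.2 to 69.4) | 7/60 × 64.15 = 7.5 points |
| All satisfied | 41/60 = 68.3% | −4.2 points |

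With 3 excluded (5%), the worst case is 36/57 = 63.2% against 36/60 = 60.0%, a gap of 3.2 points.

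For N of 30, 60 or 90, the worst-case gap is 7.5 to 8.7 points at 12% excluded and 2.8 to 4.3 points at 5%.

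**The case against.** **The SAP may refine the populations.** Protocol 9 and 9.4 leave the detailed populations to the SAP. The single sentence in Protocol 9.3 is also a rough summary: read literally, it would restrict midsection photographs to people who completed some other area. A set requiring both the midsection and another area is a natural choice for an endpoint about both, and the protocol's own evaluable populations are completer sets. So a reader might infer that the SAP overturns a deliberate protocol rule, but the documents do not go that far. What remains is that SAP 9.4.1 and 9.4.2 give different denominators for one endpoint. The version history says that the population definitions were updated, but its visible text gives no reason.

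**Nothing is lost.** A reader might infer that the answers are thrown away. They are not: they stay in the Safety Population listing, SAP 5.0 reports the population counts, and SAP 6.0 tabulates interrupted and discontinued treatments with reasons. But none of these gives a rate or CI that includes the omitted answers.

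**Few answers may be affected.** Table 6-1 sets a minimum of one midsection session, the second session is optional, each session may be spread over 7 days, and Protocol 8.2.1 lets a treatment stopped for discomfort be resumed. Participants who withdraw leave the study, so many may give no 12-week answer. This stands, and it makes 7 of 60 a high assumption. Deviation exclusions are additional, and their number is equally unknown.

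**Nothing is decided on this rate.** Also true. The 70% success rule applies to photograph identification, not to CSQ-Overall.

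**Conclusion.** The mismatch is in the current text. A key secondary rate is reported in a narrower group than the one its definition names and its questionnaire reaches, and nothing planned shows the effect. The narrowing has two parts: plan completion and the absence of significant deviations.

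The size is unknown and probably small. On the assumed 60 respondents with 7 excluded, the all-respondent rate is 1.7 points lower if half of those excluded were satisfied and 7.5 points lower if none was. The latter is a bound, not an expectation, and the exact CI is about 27 points wide.

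A reader might infer that the SAP rate is inflated. Stopping for discomfort or refusal makes that plausible, but the documents do not establish it. The gap is zero if those excluded are equally satisfied and changes sign if they are more satisfied. The case for change rests on matching the analysis to the endpoint, not on a demonstrated bias.

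**What to change.** - In SAP 9.4.2, summarise CSQ-Overall Item 1, with an exact 95% CI, in all participants who received treatment to the midsection and at least one additional area and who answered the item at the 12-week visit after final treatment.
- Keep Evaluable Population 4 as a supporting row. Beside it, report how many answers it excludes and why: plan not completed, or significant deviation or violation.
- Reconcile the population wording in Protocol 9.3 with the endpoint in 9.4.3, including participants who did not complete their only additional area.

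The schedule already collects these answers. The cost is some wording, one extra table row, and a rate that may be slightly less favourable. If the two rows agree, the added row shows that the result does not depend on the exclusions.

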## 5.0 Participant Disposition

The number of participants who are in the Enrolled Population and the number and percentage of participants who are in the Safety Population, Evaluable Population 1, Evaluation Population 2, Evaluable Population 3, and Evaluable Population 4 will be summarized. Under Evaluable Population 2, the number and percentage of participants who completed each individual treated body area (Upper Arms, Inner Thighs, Outer Thighs and Submental Area) will be summarized. The number and percentage of screen failure participants and the screen failure reasons will also be summarized for the Enrolled Population.

The number and percentage of participants who complete the study and who prematurely discontinue from study will be presented for the Safety Population; furthermore, the number and percentage of participants discontinued prematurely from study will be presented for the Safety Population by the primary reason for discontinuation as collected on the eCRF. Reasons for premature discontinuation from the study include:

- Adverse Event
- Withdrawal of consent
- Pregnancy
- Protocol Deviation
- PI Discretion
- Chronic Disease (for EU only)

- Lost to follow-up
- Other

A Listing of participant disposition will be provided for the Enrolled Population.

## 6.0 Treatment Exposure and Compliance

The total number of completed treatment cycles will be summarized using descriptive statistics (n, mean, SD, median, Q1, Q3, minimum and maximum) for combined treated body areas, by each treatment session and overall for the Safety Population, Evaluable Population 1, Evaluable population 2, Evaluable Population 3, and Evaluable Population 4. Combined treated body areas including combined upper and lower abdomens, combined right and left flanks, combined upper and lower abdomens and right and left flanks, combined right and left upper arm, combined right and left inner thigh, combined right and left outer thigh, and all combined treated body areas. The average percentage of overlapping treatment on each body area will be listed but not summarized.

The number and percentage of treatments interrupted or discontinued along with the reason will be presented for individual treated body area, and for combined treated body areas as specified in Section 6.0, by treatment session and overall for the Safety Population.

The number and percentage of participants with single, dual, triple, or quad applicators used will be summarized by country, treatment session and overall for the Safety Population.

The completed treatment plan will be summarized by country, treatment round, treatment session and overall for the Safety Population.

The study investigators are responsible for performing the study in compliance with the protocol. The treatment compliance will not be applicable in the study.

All treatment exposure data will be listed for the Safety Population.

---

## **7.0 Demographics, Baseline Characteristics, Medical History, and Prior/Concomitant Medications**

### **7.1 Demographics and Baseline Characteristics**

Demographic parameters will be summarized descriptively for the Safety Population, Evaluable Population 1, and Evaluable Population 2. Demographic parameters include age, sex (if female, childbearing potential), race, and ethnicity, where race and ethnicity are collected only at sites in US and Singapore. Demographic parameters will also be summarized descriptively by treated body area for the Evaluable Population 3.

Baseline characteristics will be summarized descriptively for the Safety Population, Evaluable Population 1, and Evaluable Population 2. Baseline characteristics include weight, height, Fitzpatrick Skin Type (I, II, III, IV, V, VI), and body mass index (BMI). Baseline characteristics will also be summarized descriptively by treated body area for the Evaluable Population 3.

Demographic and baseline characteristics will be provided in a listing for the Safety Population.

### **7.2 Medical, Surgical and/or Cosmetic History**

Medical, surgical and/or cosmetic procedural history data will be coded using the Medical Dictionary for Regulatory Activities (MedDRA). The actual version of the MedDRA will be noted in the statistical tables and clinical study report. The number and percentage of participants in each system organ class (SOC) and preferred term (PT) will be summarized for the Safety Population.

The summary table by SOC and PT will be presented with SOC in alphabetical order and PT in decreasing frequency within each SOC. If more than one medical history term is coded to the same PT for the same participant, the participant will be counted only once for that PT.

A listing will be provided for the Safety Population.

### **7.3 Prior and Concomitant Medications**

A prior medication is defined as any medication that started and stopped prior to the date of the first CoolSculpting Elite procedure.

---

A concomitant medication is defined as any medication that started prior to the date of the first CoolSculpting Elite procedure and continued after the first CoolSculpting Elite procedure, or any medication that started on or after the date of first CoolSculpting Elite procedure.

Prior and concomitant medications will be coded using the World Health Organization Drug Dictionary (WHO DD). The actual version of the WHO DD will be noted in the statistical tables and clinical study report.

The number and percentage of participants with use of prior and concomitant medications will be summarized separately, by anatomic therapeutic chemistry (ATC) class and PT for the Safety Population. The summary will be presented with ATC class in alphabetical order and PT in decreasing frequency within each ATC class. If a participant took a specific medication multiple times or took multiple medications within a specific PT, that participant would be counted only once for the PT.

A listing will be provided for the Safety Population.

#### **7.4 Concomitant Procedures**

All concomitant procedures will be listed for the Safety Population.

#### **7.5 Protocol Deviations and Violations**

A protocol deviation (PD) is any non-adherence to study procedures that does not result in additional risk to the participant. Protocol deviations will be reviewed and documented before database lock.

A protocol violation (PV) is any non-adherence to the protocol that may result in significant additional risk to the participant (eg, enrollment of a participant who does not meet the study criteria). A protocol violation can also be an event of non-adherence to GCPs that may impact participant safety (eg, failure to obtain proper consent before performing study procedures). Violations should be reported to the study sponsor and the IRB within 5 working days if they occur.

Significant PDs/PVs (equivalent to major PDs/PVs as collected in data) listed below will be identified before database lock. The number and percentage of participants with significant PDs/PVs will be summarized for the Safety Population. Significant PDs/PVs related to the following categories which impact the study conduct, data validity or integrity for the study outcomes will be included:

- Key inclusion criteria

- Key exclusion criteria
- Withdrawal criteria
- Treatment
- Concomitant medications
- Timeframe deviation

A listing will be provided for the Enrolled Population.

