## 2.3 Treatment Assignment and Blinding

Study intervention is defined as the medical device (CoolSculpting Elite System and CoolSculpting Elite applicators) intended to be administered to a study participant according to the study protocol.

At screening, after the participant has signed the informed consent form (ICF), the participant will be assigned a screening number sequentially based on the order in which the participant is screened into the study at that particular site. The participant identification number (i.e., site ID concatenated with the participant screening number) will serve as the participant identification number on all study documents.

Participants will undergo a CoolSculpting Elite treatment in an outpatient clinical setting. A treatment is comprised of timed segments of cooling (treatment cycle) followed by 2 minutes of manual massage. Treatments will be administered according to the CoolSculpting Elite user manual that has been prepared for specific countries and provided to the study sites. The CoolSculpting Elite applicators available in this study depend on country clearances and can include Curve 240, Curve 150, Curve 120, Flat 165, Flat 125, Surface 150, and Curve 80.

Blinding is not applicable to this open-label, nonrandomized study. Blinding will only be employed for photograph review by an independent panel of physician reviewers with expertise in the areas of dermatology and/or plastic surgery.

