### **9.3.2 Main Analysis of Primary Effectiveness Endpoint(s)**

The CSQ consists of 6 versions: CSQ-Midsection, CSQ-Overall, CSQ-Upper Arms, CSQ-Inner Thighs, CSQ-Outer Thighs, CSQ-Fat under chin. However, only CSQ-Midsection will be used for the primary analysis. In each version, the CSQ Item 1 is about rating the participant overall satisfaction with the results of the fat reduction procedure on the treated body area based on the following categories:

- Very satisfied
- Satisfied
- Neither satisfied nor dissatisfied
- Dissatisfied
- Very dissatisfied

The number and percentage of participants with “satisfied” or “very satisfied” on the Item 1 for the CSQ-Midsection at Week 12 (Visit 8) for participants who receive 1 treatment session, or at Week 20 (Visit 9) for participants who receive 2 treatment sessions, or at 12 weeks +14 days post treatment session 2 for participants who had their treatment session 2 rescheduled because of the CoolSculpting® Elite treatment hold in the US on / after 24th August 2021 will be summarized for the Evaluable Population 1 and the two-sided Fisher’s exact 95% CI on the percentage will be provided.

A listing will be provided for CSQ-Midsection for the Safety Population.

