## 14.0 Version History

### SAP Version History Summary

Version	Date	Summary
0.1	09 June 2021	First draft
0.2	21 June 2021	Second draft, updated based on comments from Abbvie
0.3	15 October 2021	Third draft, updated based on comments from Abbvie
0.4	04 March 2022	Fourth draft, updated based on comments from Abbvie
0.5	05 April 2022	Fifth draft, updated based on comments from Abbvie
0.6	08 April 2022	Final draft, updated based on comments from Abbvie
1.0	11 April 2022	Final version
1.1	21 July 2022	
Updated final version, changes include: Updated the definitions of Evaluable Population 1, 2, 3 and 4 (Section 4.0).
 
[REDACTED]
 
Updated participant disposition, treatment exposure, demographic and baseline characteristics, and effectiveness analyses based on comments from Abbvie (Section 5.0 to Section 9.6).

2.0	29 July 2022	Updated final version

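### SAP 7.5 lets the deviations that remove participants from the primary analysis set be settled up to database lock, without thresholds and with no described masking to the satisfaction answers

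*SAP*

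**What the plan says.** Protocol 9.3 defines the primary evaluable population as "all treated participants who completed the cryolipolysis treatment plan to the midsection and who completed the CSQ-Midsection Item 1 at 12 weeks", counted from the last session. It has no deviation exclusion.

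SAP 4.0 adds one. Members of Evaluable Population 1 must also satisfy: "and do not have any significant protocol deviation or violation". The other three evaluable populations carry the same clause. SAP 9.3.2 uses Evaluable Population 1 alone for the primary rate, which "will be summarized for the Evaluable Population 1 and the two-sided Fisher’s exact 95% CI on the percentage will be provided".

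SAP 7.5 gives the timing and the test. On timing: "Significant PDs/PVs (equivalent to major PDs/PVs as collected in data) listed below will be identified before database lock". On the test, what counts are deviations and violations "related to the following categories which impact the study conduct, data validity or integrity for the study outcomes will be included". The six categories are key inclusion criteria, key exclusion criteria, withdrawal criteria, treatment, concomitant medications and timeframe deviation. The section does not name the key criteria, set a day limit for timing or say who decides.

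SAP 2.3 states: "Blinding is not applicable to this open-label, nonrandomized study". It reserves blinding for the photograph review. SAP 9.3.3 plans no sensitivity or supplementary analysis of the primary endpoint, and SAP 9.2 rules out imputation.

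**The concern.** This point is about how deviators are chosen, which is a different question from whether they should be excluded. The primary result is one proportion, so each borderline classification keeps or removes one participant whose answer may already be known. If the person deciding can see that answer, selection on the outcome is possible, and the exact interval does not reflect it.

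Borderline calls are foreseeable:

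- **Weight:** the schedule of activities rechecks eligibility at Visits 8 and 9, when the primary questionnaire is completed. Inclusion criterion 8 asks participants to keep weight within 5%. Whether a breach is key is not stated, and weight change could plausibly relate to satisfaction.
- **Timing:** visit windows are written as a day plus an allowance, so the status of an early visit is unclear. The US treatment hold moved some second sessions.
- **Concomitant products:** Protocol 6.5.1 prohibits several common supplements. When their use becomes significant is not stated.

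**Working it through.** **1. The plan's own figure.** Inputs from SAP 2.4: n = 96, rate 63.9%, two-sided 95% Clopper-Pearson interval, width 0.2, attrition 12%. With x = 96 × 0.639 = 61.344:

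- Lower limit = Beta quantile(0.025; x, n − x + 1) = 53.46%.
- Upper limit = Beta quantile(0.975; x + 1, n − x) = 73.46%.
- Width = 0.19996, and 96 is the smallest n with a width of 0.2 or less.
- 96 / 0.88 = 109.1, rounded up to 110.

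The planning figures reproduce. The planned half-width is 0.2 / 2, or 10 points.

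**2. How far exclusions can move the rate.** With X satisfied among N and k participants removed, the rate lies between (X − k)/(N − k), if all k were satisfied, and X/(N − k), if none were. The documents give no expected number of exclusions, so k is an assumption.

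Start from X = 61, N = 96 (63.5%, the whole count nearest the planning rate). The exact interval is 53.1% to 73.1%.

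| k | All removed not satisfied | All removed satisfied | Shift (points) |
|---|---|---|---|
| 1 | 61/95 = 64.2% | 60/95 = 63.2% | +0.7 / -0.4 |
| 5 | 61/91 = 67.0% | 56/91 = 61.5% | +3.5 / -2.0 |
| 10 | 61/86 = 70.9% | 51/86 = 59.3% | +7.4 / -4.2 |

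These shifts are all smaller than the 10-point half-width.

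**3. A second starting rate.** Protocol 2.2 reports 89.6% in an earlier study. From 86/96 = 89.6% (exact interval 81.7% to 94.9%):

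- k = 5 gives 81/91 = 89.0% to 86/91 = 94.5%, a shift of -0.6 / +4.9 points.
- k = 10 gives 76/86 = 88.4% to 86/86 = 100%, a shift of -1.2 / +10.4 points. The upper end requires that every one of the ten participants not satisfied is removed.

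**4. Exclusions unrelated to the answer.** The expected rate would not move. From 61/96 only the interval would widen, to about 20.6 points at k = 5 and 21.2 at k = 10, against the planned 20.

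**5. Which schedule defines timing.** In protocol Table 1-1, Visit 6 ends at Day 56 + 14 = Day 70 and Visit 9 at Day 140 + 14 = Day 154. The SAP 2.2 schedule adds windows for participants rescheduled because of the US treatment hold, and SAP 4.0 keeps them in Evaluable Population 1. A program using Table 1-1 would flag those whose visits fell after Day 70 or Day 154. Protocol 4.1 also allows a session to be completed within 7 days. A session begun on Day 70 can therefore finish at about Day 76, and 76 + 84 = Day 160, past Day 154.

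**The case against.** The case against is substantial, and much of it stands as a limit on the point.

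- **The discretion is bounded.** SAP 7.5 equates significant with major as collected in the data, so some grade is recorded with each deviation. Violations go to the sponsor and ethics board within 5 working days, and Protocol 6.4 has deviations entered on the case report forms. Many entry and treatment deviations will be known before the Week 12 or 20 answer exists. SAP 7.5 also supplies only one condition for membership; plan completion and, for Evaluable Population 1, questionnaire completion supply the rest. Even so, the grading has no thresholds and can be finalised up to lock.
- **Absence of masking is inferred from silence.** SAP 2.3 is about treatment blinding, not about access during data review. An unpublished procedure may exist.
- **Exclusions can be traced.** Significant deviations are counted and listed (SAP 7.5), population sizes are reported (SAP 5.0), and CSQ-Midsection is listed for the Safety Population (SAP 9.3.2). That allows a check from listings, but no rate without the exclusion is planned.
- **No hypothesis is tested.** The harm is possible bias in an estimate, not type I error.

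Three stronger readings are tempting, and the documents do not support them. A reader might infer from the version history, which shows the evaluable populations redefined in version 1.1 of 21 July 2022 after version 1.0 of 11 April 2022, that exclusions were shaped by results. That entry says nothing about how deviations were classified and is partly redacted. No lock date is given, and Protocol 9.4 allows the SAP to be finalised up to lock. A reader might also set the full ten-exclusion spread (10/86 = 11.6 points) against the 10-point half-width. That is not like for like: a full spread belongs beside the full width of 20. Nor do the documents show that anyone selected on the answers.

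**Conclusion.** The concern holds in bounded form. Membership of the primary analysis set depends partly on a classification that has no thresholds, can be finalised up to database lock in an open-label study, and has no described separation from the primary outcome. The SAP's only stated safeguard is the timing before lock, and no supplementary rate is planned that would show the effect.

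Starting from 61/96, the worst-case shift is +3.5 / -2.0 points for five exclusions and +7.4 / -4.2 for ten, against a half-width of about 10. These bounds rest on assumed exclusion counts, on a rate near the planning value, and on every exclusion going the same way. They do not predict actual bias. At a higher rate such as 89.6%, the possible upward shift is larger.

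This is an improvement worth making, not a flaw that invalidates the analysis. If a masked review already exists, a sentence in SAP 7.5 describing it would settle the masking part.

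**What to change.** 1. Add to SAP 7.5 that significant deviations and violations are classified from a deviation listing that carries no CSQ, CGPQ, CPIQ or photo-review data, by staff who do not view those data. The list is signed, dated and frozen before CSQ Item 1 and photo-review data are released for analysis.
2. Flag out-of-window visits by program from the SAP 2.2 schedule of activities, including its provisions for participants rescheduled because of the US treatment hold, and not from protocol Table 1-1. Allow for the 7-day session-completion window and state the day from which follow-up is counted. Whether a flagged visit is significant is then decided in the same masked review.
3. Add to SAP 9.3.3 a supplementary primary rate without the deviation exclusion, in the Protocol 9.3 evaluable set with the SAP's timing for rescheduled participants.

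The cost is SAP wording, one restricted data view, one extra table row and a short delay in releasing outcome data. Questionnaires are on paper (Protocol 8.1.1) and photo reviews are on separate forms (Protocol 8.1.2), so both can be held back. Monitors verify source data and may see the questionnaires, so the restriction has to apply to whoever makes the final classification.
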